### ***6.3.4. Last Observation Carried Forward (LOCF)***

A last observation analysis is performed by carrying forward the last postbaseline assessment for continuous measures. For patients discontinuing the study, the last nonmissing postbaseline observation before discontinuation will be carried forward to the corresponding endpoint for evaluation.

After LOCF imputation, data from patients with nonmissing baseline and at least 1 postbaseline observation will be included in the analyses. These LOCF analyses help ensure that the

maximum number of randomized patients who were assessed postbaseline will be included in the analyses.

#### **6.3.5. *Mixed-effects Model Repeated Measures (MMRM)***

For continuous variables with multiple postbaseline measurements, the primary analysis will be MMRM with the missing-at-random (MAR) assumption for handling missing data. This analysis considers both missingness of data and the correlation of the repeated measurements. No additional imputation methods will be applied to the MMRM analysis.

#### **6.3.6. *Highest Disease States Imputation (HDSI)***

For the analyses related to National Institute of Allergy and Infectious Diseases (NIAID) ordinal scale, the following imputation will be considered if applicable.

For patients whose data is missing during the hospitalization period (not yet recovered), a score of 2, which is the worst value for a hospitalization status, will be used for imputation.

For patients whose data is missing after recovery or discharged, a score of 7, the worst value for a recovery or nonhospitalized status, will be used for imputation.

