The maximum total duration of study participation for each participant of the treatment group is 12 weeks. See the SOA for the treatment group in Section 1.3.2.

This table describes the visit types for the prevention population for this study.

Study Day	Activity	Visit Type
0,1	Follow SoA	Onsite
8, 15, 22, 29, 36, 43, 50, 57	Follow SoA Vital signs*	Onsite or Home (Virtual [record collection] if hospitalized)

Daily 2 - 57	Vital signs and symptoms questionnaire daily* Vital signs, clinical status, and concomitant procedures for hospitalized participants.	Onsite or Home (Virtual [record collection] if hospitalized)
ETV and follow-up (85, 141, 169)	Follow SoA	Onsite or Home

*Collected via direct data capture for onsite or home visits only.

This table describes the visit types for the treatment population for this study.

Study Day	Activity	Visit Type
0, 1	Follow SoA	Onsite
8, 29	Follow SoA Vital signs*	Onsite or Home (Virtual [record collection] if hospitalized)
Daily 2-29	Vital signs, clinical status, and concomitant procedures for hospitalized participants.	Virtual (record collection) if hospitalized
ETV and follow-up (85)	Follow SoA	Onsite or Home

*Collected via direct data capture for onsite or home visits only.

Hospitalization

If a participant is hospitalized, efforts will be made to retrieve hospital records and report procedures and assessments according to the SoA, as feasible.

Definitions for COVID-19 Severity

This table gives the definitions for COVID-19 severity of illness for those participants who are SARS-CoV-2 positive as determined by standard RT-PCR assay or equivalent test.

Table 1 Definitions for COVID-19 Severity

Severity	Description
Mild	Mild symptoms that could include: 
 fever, cough, sore throat, malaise, headache, muscle pain, gastrointestinal symptoms, without shortness of breath or dyspnea AND No clinical signs indicative of Moderate, Severe, or Critical Severity
Moderate	Symptoms of moderate illness with COVID-19, which could include any symptom of mild illness or shortness of breath with exertion AND Clinical signs suggestive of moderate illness with COVID-19, such as: 
 respiratory rate \geq 20 breaths per minute,

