#### 6.16.1.2. Worst NIAID Score

The lowest daily value from Day 1 through the end of the Evaluation Period for a patient on the NIAID ordinal scale will be analyzed using a nonparametric rank-sum test (such as Mann-Whitney or van Elteren test) adjusting for facility and for the randomization stratification factors. Missing data will be imputed using HDSI, as described in Section 6.3.6. Mean value by treatment group will be plotted over time. This comparison will be made on the Prevention and Treatment populations.

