## Appendix 1. NIAID Scoring Scale

---

The National Institute of Allergy and Infectious Diseases (NIAID) scoring scale will be assessed daily and defined as the lowest score achieved for that day.

The scoring is based on the clinical status of the patient as described below.

NIAID Score	Description
1	Death
2	Hospitalized, on invasive mechanical ventilation or extracorporeal membrane oxygenation (ECMO)
3	Hospitalized, on noninvasive ventilation or high flow oxygen devices
4	Hospitalized, requiring supplemental oxygen
5	Hospitalized, not requiring supplemental oxygen - requiring ongoing medical care (COVID-19-related or otherwise)
6	Hospitalized, not requiring supplemental oxygen - no longer requires ongoing medical care
7	Not hospitalized, limitation on activities and/or requiring home oxygen
8	Not hospitalized, no limitations on activities

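### Worst NIAID score: because the lowest daily value is taken after HDSI, one missing pre-recovery inpatient day gives a survivor the ventilation/ECMO score of 2

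*SAP*

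**What the plan says.** SAP 6.16.1.2 takes as the endpoint "The lowest daily value from Day 1 through the end of the Evaluation Period for a patient on the NIAID ordinal scale" and compares it between arms by a rank-sum test in the Prevention and Treatment populations. On missing values it is unconditional: "Missing data will be imputed using HDSI, as described in Section 6.3.6".

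SAP 6.3.6 introduces HDSI more loosely, saying that "the following imputation will be considered if applicable". Its inpatient rule opens "For patients whose data is missing during the hospitalization period (not yet recovered), a score of 2" and continues "which is the worst value for a hospitalization status, will be used for imputation". A companion rule covers the time after that: "For patients whose data is missing after recovery or discharged, a score of 7".

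SAP Appendix 1 scores participants daily, with lower numbers worse. Score 1 is death and 2 is invasive mechanical ventilation or ECMO. Scores 3 to 6 are the less severe inpatient states, and 7 and 8 are states outside hospital.

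Protocol 4.1.2 says that when a participant is hospitalized "efforts will be made to retrieve hospital records and report procedures and assessments according to the SoA, as feasible". Protocol 1.3 and 8.2.5 list oxygen, ventilation and ECMO among the items to be recorded for inpatients.

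**The concern.** A worst-case fill is a familiar choice when each day is analysed in its own right. Here it is combined with a minimum over days, and a minimum is decided by its single lowest entry. One filled day therefore overrides every observed day of the stay. Whether a participant is reported at score 2 can depend on whether one day's record was retrieved, not on anything seen in the patient.

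HDSI as written does not look at neighbouring observed scores, does not separate an isolated gap from a lost record, and sets no minimum length of gap. The SAP specifies no analysis of this endpoint without it.

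At stake is the description of severity among inpatients, which is the stated objective of the endpoint. SAP 6.12.5 separately summarizes mechanical ventilation from the recorded oxygen source. The same report could show several participants with a worst score of 2 and fewer, or none, recorded as ventilated or on ECMO.

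**Working it through.** The plan states no figure on this point, so there is none to reproduce. The check applies the SAP's own rules and then asks how often they would bite.

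**1. The mechanism (SAP 6.16.1.2, 6.3.6 and Appendix 1; no assumption about rates)**

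- Inpatient scores 5, 5, [missing], 5, 5, 6. Observed minimum = 5. With HDSI: min(5, 5, 2, 5, 5, 6) = 2.
- Inpatient scores 4, 4, [missing], 4, 5. Observed minimum = 4. With HDSI: min(4, 4, 2, 4, 5) = 2.

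**2. Who is affected**

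- A participant who dies: min(1, 2) = 1, unchanged.
- A survivor observed on invasive ventilation or ECMO: min(2, 2) = 2, unchanged.
- A survivor whose lowest observed score is 3, 4, 5 or 6: becomes 2.
- A day missing after recovery or discharge takes 7, so it cannot produce a 2. Recovery is not defined on this scale, so a missing day for an inpatient at score 6 could fall under either rule.

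**3. How often, if days go missing independently**

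Neither the missing-day rate m nor the length of stay L is in the documents. Both are assumed. The chance of at least one missing day is 1 − (1 − m)^L:

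| Missing days (m) | L = 3 | L = 7 | L = 10 | L = 14 |
|---|---|---|---|---|
| 2% | 5.9% | 13.2% | 18.3% | 24.6% |
| 5% | 14.3% | 30.2% | 40.1% | 51.2% |
| 10% | 27.1% | 52.2% | 65.1% | 77.1% |

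For example, 1 − 0.95^7 = 0.302. These are chances of a gap. They equal chances of a changed score only for survivors with an observed worst of 3 to 6, and only if every inpatient day counts as not yet recovered.

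**4. How often, if whole records are lost**

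A stay is then either fully observed or fully missing, and the affected share is about the record-loss rate r, whatever the length of stay. Take an illustrative 20 surviving inpatients with 7-day stays, none ventilated or on ECMO:

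| Rate | Independent days | Whole records |
|---|---|---|
| 5% | 20 × 0.302 = 6.0 | 20 × 0.05 = 1 |
| 10% | 20 × 0.522 = 10.4 | 20 × 0.10 = 2 |

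The pattern of missingness matters as much as its rate, and the documents settle neither.

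**5. Effect on the rank-sum test**

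Moving an inpatient from 3–6 down to 2 reorders that person only among the hospitalized. Anyone at 7 or 8 was already ranked better and stays so. If most participants are never hospitalized, the overall test changes less than the reported distribution.

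**The case against.** The strongest reply is that SAP 6.3.6 is hedged, is limited to participants not yet recovered, and never mentions single days inside an otherwise observed stay. This stands in part. A reader might infer that every missing hospital day must become 2; the text does not go that far. But 6.16.1.2 applies HDSI to this endpoint without a hedge, and the scores are daily, so the day-by-day application is the natural reading for an analyst. The two sections at least need to agree.

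Second, gaps may be rare. The protocol asks for daily clinical status in hospitalized participants and accepts hospital records as documentation. Its wording on retrieving records shows that gaps are possible, not that they are common. This stands, and it is why the rates above are only assumptions.

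Third, a reader might infer that scores 3 to 6 all but disappear among inpatients. The figures do not support that: at 5% missing and a 7-day stay, about 70% of stays have no gap even under independence, and more under whole-record loss.

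Fourth, SAP 6.12.5 and 6.16.2.5 report ICU admission and ventilation separately, so an attentive reader could notice the mismatch. That is true, but those outputs do not correct this endpoint.

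Fifth, worst-case imputation is deliberate, and using observed scores leans the other way by treating an unrecorded day as no worse than the recorded ones. That is fair, and it is why the worst-case version should be kept as a sensitivity analysis. It is not automatically conservative between arms, however: when days go missing independently, longer stays have more chances of a gap.

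**Conclusion.** The point holds as a limited defect in an exploratory endpoint. Under SAP 6.16.1.2 with 6.3.6, a single missing, not-yet-recovered inpatient day is enough to give a survivor with an observed worst score of 3 to 6 the score for invasive ventilation or ECMO. That conclusion follows from the text and needs only the day-by-day application of HDSI.

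The size is uncertain. For a 7-day stay the chance of at least one gap is 13% to 52% if days are missing independently at 2% to 10%. If whole records are lost, it is about the record-loss rate.

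A reader might infer that the between-arm comparison is seriously distorted, or that the trial's main results are touched. The documents support neither. The endpoint is outside the testing scheme in SAP 6.5, deaths and truly ventilated survivors keep their scores, and the rank-sum test changes less than the distribution. No primary or key secondary conclusion is affected.

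**What to change.** In SAP 6.16.1.2:

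- Define the worst score as the lowest observed score whenever a stay has at least one observed daily score. Use the recorded ventilation, ECMO and oxygen entries to fill missing days where they are available.
- In the main analysis, apply HDSI (score 2) only to stays with no observed score and no procedure entry.
- Report HDSI for all missing inpatient days as a sensitivity analysis.

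In SAP 6.3.6, replace the conditional introduction with wording that matches 6.16.1.2, and say what counts as recovered on this scale.

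The cost is SAP wording and a small change to the derivation; no new data are needed. There is one small downside. Procedure entries may be missing on the same days as the scores, so a brief ventilation on a day with neither could be missed. The sensitivity analysis bounds that. Records lost entirely, with no procedure entry, would still be scored 2 in the main analysis, so the gain is for stays with partial data.

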### **6.4. Multicenter Studies**

[figure not shown]
Differences between study centers will not be a feature of the statistical analyses for this study. Baseline variables and demographics may be described by site.

Individual center results may be presented, where appropriate, when the centers have sufficient numbers of patients to make such analysis potentially valuable. The possibility of qualitative or quantitative treatment-by-center interaction may be explored.

### **6.5. Multiple Comparisons/Multiplicity**

To control for multiplicity, a graphical testing sequence approach will be used to test the primary and key secondary endpoints within each part of the study.

For Part 1, the primary endpoint will be tested at the two-sided 0.05 significance level. If the primary endpoint is successful, then the secondary endpoint of incidence of SARS-CoV-2 infection will be tested at the two-sided 0.01 significance level. The secondary endpoint of incidence of moderate-or-worse severity COVID-19 will be tested simultaneously at the two-sided 0.04 significance level. If either secondary endpoint is successful, the other secondary endpoint will be tested at the two-sided 0.05 significance level. This testing scheme is displayed in [Figure PYAD.6.1](#).

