Part 3 objectives are exploratory and therefore described in [Section 3](#).

Overall Design

Study J2X-MC-PYAD is a randomized, double-blind, placebo-controlled, prophylaxis study to evaluate the efficacy and safety of intravenous LY3819253, alone and in combination with LY3832479, in preventing SARS-CoV-2 infection and COVID-19, compared to placebo. An independent Data Safety Monitor Board (DSMB) will actively monitor interim data to make recommendations about early study closure or changes to sample size.

Disclosure Statement: This is a three-part, 9-arm interventional study that is double-blinded.

Number of Participants:

For Part 1, a total of approximately 1700 participants (intent-to-treat [ITT] population) will be randomly assigned to study intervention such that approximately 1300 SARS-CoV-2 RT-PCR and serology negative participants are randomized in the study with the goal of achieving approximately 33 events (in each of the primary and key secondary endpoints) in the prevention population.

For Part 2, a total of approximately 2000 participants will be randomly assigned to study intervention based on rapid point of care (POC) testing such that approximately 1700 participants SARS-CoV-2 RT-PCR and serology negative participants are randomized in the Prevention Cohort with the goal of achieving approximately 56 events on each of the primary and key secondary endpoints.

Part 3 will enroll at least 30 participants and up to approximately 500 participants randomized to study intervention.

The maximum sample size for this study is approximately 5000 participants in the ITT population.

Intervention Groups and Duration:

Participants will receive one intravenous infusion of study intervention.

The maximum total duration of study participation for each participant of the prevention groups is 24 weeks.

The maximum total duration of study participation for each participant of the treatment group is 12 weeks.

Part 1:

Eligible participants will be randomized to one of two arms: placebo or LY3819253 4200 mg.

Participants will continue to enroll to Part 1 until the needed events for the primary and key secondary endpoints are achieved and the minimum number of residents enroll.

The evaluation period for Part 1 is 8 weeks, with follow-up to 24 weeks.

Part 2:

The Sponsor will decide when to trigger activation of Part 2. Activation of Part 2 will be communicated to sites.

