## **5.2. Determination of Sample Size**

For Part 1, an estimated 33 events are needed to show superiority of LY3819253-4200mg over placebo in each of the primary and key secondary endpoints, using the formula by Schoenfeld (1983). An average sample size of approximately 1300 participants who are SARS-CoV-2 PCR negative and serology negative at baseline is expected to obtain the needed number of events for each endpoint.

For Part 2, an estimated 56 events in the Prevention Cohort are needed to show superiority over placebo for either LY3819253-700mg or LY3819253-350mg+LY3832479-700mg in each of the primary and key secondary endpoints. Approximately 2000 participants on average will be randomly assigned to study intervention such that approximately 1700 participants are randomized in the Prevention Cohort with the goal of achieving approximately 56 events on each of the primary and key secondary endpoints.

The maximum sample size for this study is approximately 5000 participants in the intent-to-treat (ITT) population.

Participants will be residents and staff of skilled nursing and assisted living facilities. Globally, there are many reports of the rapid spread of COVID-19 amongst residents of skilled nursing facilities following identification of an index case, with high associated rates of morbidity and mortality (Arons et al. 2020; Grabowski). Given that residents at these facilities are at higher risk for having a more severe disease course of COVID-19, this will be an important population to participate in the study. Therefore, a minimum of 300 residents will be enrolled.

Operationally, this will be accomplished, when possible, by identifying facilities where approximately half of the participants interested in the study are residents.

For sample size determination for Part 1, the following assumptions were used:

- 1) two-sided significance level of 0.05;
- 2) 90% power for the primary and key secondary endpoints;
- 3) an 8-week placebo group event rate of 4.0% for moderate or worse severity COVID-19;
- 4) a risk ratio of 0.33 between LY3819253 and placebo in terms of the primary and key secondary endpoints.

For sample size determination for Part 2, the following assumptions were used:

- 1) two-sided significance level of 0.025;
- 2) 90% power for the primary and key secondary endpoints;
- 3) an 8-week placebo group event rate of 5.3% for moderate or worse severity COVID-19;

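### Part 1: the 90% power stated for the key secondary endpoints ignores the gate and the alpha split, and at the stated 33 events the infection endpoint falls short of it

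*SAP*

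**What the plan says.** SAP 5.2, in the same terms as protocol 9.2, sizes Part 1 from a "two-sided significance level of 0.05", "90% power for the primary and key secondary endpoints" and "a risk ratio of 0.33 between LY3819253 and placebo in terms of the primary and key secondary endpoints". The only placebo rate given is "an 8-week placebo group event rate of 4.0% for moderate or worse severity COVID-19". The result, by Schoenfeld's formula, is that "an estimated 33 events are needed to show superiority of LY3819253-4200mg over placebo in each of the primary and key secondary endpoints". The protocol synopsis repeats the target: about 1300 baseline-negative participants "with the goal of achieving approximately 33 events (in each of the primary and key secondary endpoints) in the prevention population".

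SAP 6.5 sets the tests. The primary is tested at two-sided 0.05. If it succeeds, "the secondary endpoint of incidence of SARS-CoV-2 infection will be tested at the two-sided 0.01 significance level", and moderate-or-worse COVID-19 is tested at the same time at 0.04. If either succeeds, the other may be tested at 0.05.

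SAP 6.1.5.1 triggers the Part 1 lock at 33 moderate-or-worse cases (with at least 300 residents enrolled), with the declared aim that the primary and key secondary endpoints are all well powered. If those cases accrue slowly, the lock may instead follow 36 infections within 4 weeks, and then only the primary is evaluated at that lock.

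**The concern.** The sizing sections treat each key secondary as if it were tested alone at 0.05. Under SAP 6.5 neither key secondary starts at 0.05, and neither is tested at all unless the primary succeeds. Neither sizing section mentions the gate, the split or the recycling. The protocol leaves the final testing sequence to the SAP, and the SAP chose a split without revisiting its own section 5.2.

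What is at stake is interpretation. If infection by Day 29 missed significance, a reader would judge the miss against a 90% power claim that does not describe the test actually carried out.

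**Working it through.** **Inputs.** Two-sided alpha 0.05, power 90%, risk ratio 0.33, placebo rate 4.0% and 33 events (SAP 5.2); 1:1 allocation (protocol 6.3); alphas 0.05, 0.04 and 0.01 with recycling to 0.05 (SAP 6.5).

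**Reproducing the 33.** With 1:1 allocation, Schoenfeld's formula is d = 4(z₁₋α/₂ + z₁₋β)² / (ln θ)², where (1.960 + 1.282)² ≈ 10.51. The active-arm rate is 0.33 × 4.0% = 1.32%.

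- θ as the risk ratio, 0.33: 4 × 10.51 / 1.1087² = 34.2.
- θ as the implied hazard ratio, ln(1 − 0.0132)/ln(1 − 0.04) = 0.3255: 33.4.
- θ as the implied odds ratio, (0.0132/0.9868)/(0.04/0.96) = 0.3210: 32.6, which rounds up to 33.

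So 33 is the right count for 90% at two-sided 0.05, to within rounding and the choice of effect scale.

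**Power at 33 events, each test alone.** Power = Φ(√33/2 × |ln θ| − z₁₋α/₂), with z = 1.960, 2.054 and 2.576 for alpha 0.05, 0.04 and 0.01. The first term is 3.184, 3.224 and 3.264 for the three values of θ.

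| θ | alpha 0.05 | alpha 0.04 | alpha 0.01 |
|---|---|---|---|
| 0.33 | 89.0% | 87.1% | 72.9% |
| 0.3255 | 89.7% | 87.9% | 74.2% |
| 0.3210 | 90.4% | 88.7% | 75.4% |

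For 90% power alone, the events needed are 35-37 at 0.04 and 47-49 at 0.01.

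**Power under the whole scheme.** I simulated the three test statistics as correlated normals with unit variance and means √d/2 × |ln θ|, then applied the gate, the split and the recycling. Correlation between two statistics was set to shared events / √(events₁ × events₂). Every moderate-or-worse case is also a primary case, so that correlation is √(33 / primary events). The overlap of infection with primary events is not in the documents. I assumed that the shared events are 50-80% of the smaller of the two counts. Moderate-or-worse has 33 events throughout. Results are for θ = 0.33 and 0.3255, with 400,000 draws per scenario.

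| Primary events | Infection events | Infection power | Moderate-or-worse power |
|---|---|---|---|
| 33 | 33 | 81-85% | 88-89% |
| 40 | 33 | 83-85% | 87-88% |
| 45 | 33 | 84-86% | 88-89% |
| 40 | 40 | 88-89% | 87-88% |
| 42 | 42 | 89-91% | 88-89% |
| 45 | 45 | 91-92% | 88-89% |

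Using the odds ratio 0.3210 adds about one point to most of these figures. With 33 infections the results centre on 82-85%; the outer values of 81% and 86% come from the extremes of the assumed overlap and primary count. The primary count matters because gated power cannot exceed the primary's own power, which is 89-90% at 33 events.

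**The case against.** There are four fair objections.

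**The 0.01 is only a starting level.** Infection moves to 0.05 once moderate-or-worse succeeds, which is likely. This stands. A reader might take 73-75% as the power of the infection test, but that figure ignores recycling and should not be the headline.

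**Moderate-or-worse is barely affected.** This also stands. A reader might infer that the gate pulls this endpoint down to about 80%. Treating its statistic as independent of, or loosely correlated with, the primary's does give figures near 79-84%, but that contradicts the endpoint definitions. If both endpoints had 33 events, they would be the same 33 participants and the gate would cost nothing. If the primary had more, the gate would be easier to pass. The loss is 1-2 points against 89-90% at 0.05.

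**Infections will probably exceed 33 when the lock fires.** The 33 in the trigger counts moderate-or-worse cases, and the fallback envisages infections reaching 36 while those cases lag. This is plausible but not guaranteed: infection is counted over 4 weeks and moderate-or-worse over 8, and no infection rate is stated. The plan's own claim is made at 33.

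**Part 2 is different.** It is sized at 0.025, so the premise of a 0.05 design alpha does not carry over. The point is limited to Part 1.

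**Conclusion.** The stated Part 1 power does not hold for infection by Day 29 at the stated 33 events. It is about 82-85% with the gate and recycling, a shortfall of roughly 5-8 points against 90%. It closes at roughly 42-45 infections, provided primary events are as numerous. For moderate-or-worse COVID-19 the figure is about 87-89%, close to what was claimed.

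These results rest on the plan's risk ratio of 0.33 applying to all three endpoints, on nesting of moderate-or-worse cases within primary cases, and on assumed overlap and event counts for infection, which the documents do not give.

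Two stronger readings are not supported. The documents do not show that the infection test will be underpowered in practice, because its event count is unknown. Nor is there any loss of type I error control: the gate, split and recycling protect the Part 1 error rate. The primary's own 90% at 0.05 is also unaffected.

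**What to change.** In protocol 9.2 and SAP 5.2:

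- Keep 90% power at two-sided 0.05 with 33 events for the Part 1 primary only.
- Say that the sizing did not account for the gate or for the 0.04/0.01 split with recycling.
- Restate key secondary power under SAP 6.5: about 87-89% for moderate-or-worse at 33 events; for infection, about 82-85% at 33 events, 88-89% at 40 and 91-92% at 45, the last two with equal primary events.
- State the assumed correlations or overlap and, if the sponsor has one, the expected infection count.
- Bring the event target in the synopsis into line.

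The cost is wording only. Sample size, lock trigger, alpha allocation and analysis stay as they are. The stated power for infection becomes less favourable unless the sponsor can justify an expected count of about 42-45 or more.
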